The primary goal of this study is to test the effect of replacing the low levels of androgen in KS boys in an attempt to mimic the testosterone production that occurs normally in boys. Clinical support for androgen deficiency occurring earlier in childhood in KS boys than previously thought comes from the poor growth of the penis throughout childhood in these boys. The "standard of medical care" for initiating testosterone replacement therapy in KS males has typically been at age 11 or 12 years or older (59). Testosterone treatments in KS teenagers or adults results in appropriate virilization with increased muscle mass, more masculine body contour, increased body hair, penile growth, and amelioration of eunuchoidal tendencies.

Typically, adult replacement doses of 200 mg of testosterone esters such as testosterone enanthate or cypionate are given every two weeks and newer formulations utilizing the intradermal or oral route are also available in relatively high adult-level, replacement dosages. There are relatively few options for lower dose androgen replacement. One attractive consideration is the oral androgen oxandrolone which has been used safely in boys with delayed puberty and in girls with Turner syndrome for over twenty years and is FDA approved for children and adults for the indication of wasting (60-62). Oxandrolone safely increased muscle mass in prepubertal boys with constitutional delay of growth (63). We propose a two-year clinical trial using two doses of oxandrolone versus placebo in young KS boys, ages 4-12 years (see below).

RESEARCH DESIGN

Study Design: This study consists of a clinical trial composed of an eligible subset of KS boys ages 4-12 years. The randomized design excludes bias in the assignment of patients to the treatment group and ensures optimal matching of the treatment group, which includes: 1. Oxandrolone (0.06 mg/kg PO, daily), or 2. oral placebo. The PI, patients, and research assistant will be blinded as to whether the oral medication is oxandrolone or placebo. The randomization is performed by the research pharmacy.

Study Population: For the clinical trial, KS boys ages 4-12 years will be randomly assigned to one of two treatment groups (androgen versus no androgen). We will recruit 180 males (60 per year for 3 years) assuming an approximate 30% drop out rate, to accrue a total of 120 patients for the clinical trial substudy.

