1. Skeletal x-rays of the hands will be obtained for all subjects. Bone age will be determined according to the method of Greulich and Pyle (69).

Cognitive Outcome summary scores (To be age-appropriate):

1. General Cognition summary score (KS males, ages 2-60)
 - a. The Differential Ability Scales-(DAS)
2. Language summary score (age-appropriate):
 - Phonological
 - a. Comprehensive test of Phonological Processing (CTOPP).
 - Verbal Memory
 - a. California Verbal Learning Test-Children's Version (CVLT)
 - b. Children's Memory Scale (CMS)-story memory.
 - Expressive
 - a. Expressive one word vocabulary test
 - b. Rapid naming (NEPSY)
 - c. Test of language Competence (TLC) – Oral Expression
 - Receptive
 - a. Peabody Picture Vocabulary Test (PPVT)
 - b. Token Test
3. Working memory/Executive function/Attention summary score
 - a. Digit span backwards (DAS)

- b. Connors' Continuous Performance Test II (CPT II) and Kiddie Version (K-CPT)
- c. Connors' Rating Scales-Revised
- d. Verbal Fluencies-NEPSY(semantic)
- e. Design fluency-NEPSY

4. Motor function summary score
 - Strength
 - a. Bruininks-Oseretsky Test of Motor Proficiency
 - Fine motor
 - a. Bruininks-Oseretsky Test of Motor Proficiency (BOTMP)-Fine Motor Composite
 - Gross Motor
 - a. Bruininks-Oseretsky Test of Motor Proficiency (BOTMP)-Gross motor composite
 - b. NEPSY-praxis
5. Self-image summary score-Males less than 21 years of age
 - Social Function (Competence)
 - a. Behavior Assessment System for Children (BASC)
 - b. Child Behavior Checklist (CBCL)
 - Affect and Behavior
 - a. Revised Child's Manifest Anxiety Scale (RCMAS)

IV. Clinical trial substudy: Boys with Klinefelter's syndrome will enter the study at ages 4-12 years. At baseline, they will have a history and physical examination, cognitive and behavioral assessment, and further genetic evaluation. All potential subjects will have a full screening to determine eligibility before randomization. They will be randomized (double-blind) to one of two treatment groups: oxandrolone 0.06 mg/kg/day, or placebo control for two years. All subjects will be evaluated for safety at baseline, 3, 6, 12, 18 and 24 months, and after one and two years for end-point efficacy (cognitive and behavioral assessment).

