The KS boys will be seen at 3-6-month intervals for the two-year duration of the study. On each visit, boys will receive a careful history and physical examination to include assessment of Tanner staging (73) for pubic hair development (Tanner 1 = prepubertal-Tanner 5 = fully mature) and measurement of penile length and testicular volume. At baseline, three, and every six months thereafter, we will measure height, weight, bone age (X-ray); fasting blood work to include complete blood count, serum glucose, liver function tests (SGPT), lipid panel, thyroid studies, testosterone, and free testosterone (the active form of testosterone) levels. LH, FSH and estradiol will be measured yearly. At baseline and after one year, each boy will undergo a battery of cognitive tests that will take approximately 5 to 7 hours (see below).

The form of androgen will be the oral, nonaromatizable androgen oxandrolone. This androgen is FDA-approved for the indication of wasting and has been used safely for the past 30 years to stimulate growth in girls with Turner syndrome without virilization or major side effects. The dose, 0.06 mg/kg/day, was chosen because of the extensive previous experience with the dose of 0.06 mg/kg/day used in girls with Turner syndrome. Children will be monitored closely for signs of virilization including acne, voice changes,

development of pubic hair, and excessive bone age advancement. Since oxandrolone is nonaromatizable and cannot be converted to estradiol, we do not expect any feminizing side effects such as breast development to occur.

Safety results necessitating an approximate 10-50% reduction in medication dose or stopping the medication:

1. Bone age advancement exceeding 12 months per 6-month interval, with bone age exceeding chronologic age.
2. Signs of early pubertal development for age, including pubic hair development in boys less than 8 years of age.
3. Systolic blood pressure exceeding 95th %ile for age.
4. Diastolic blood pressure exceeding 95th %ile for age.
5. LDL cholesterol greater than 159 mg/dl.
6. HDL-C less than 20 mg/dl.
7. SGPT exceeding twice the upper limit of normal.
8. Dose can be lowered at the discretion of the investigator for other reasons such as rapid growth.

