The oxandrolone dosage cannot be reduced by precisely 50% because of the nature of the oxandrolone tablets that come in a single strength, 2.5 mg. The 2.5 mg pill is scored and could be accurately split to the 1.25 mg dose. The 1.25 mg dose cannot be accurately split further. Thus, according the criteria listed above, we could reduce the 3.75 mg dose to 2.5 mg and the 2.5 mg dose to 1.25 mg. Dose reduction will therefore range from approximately 10-50%, depending on the weight of the child. If the dose needs to be reduced to less than 1.25 mg/day, we will change from daily to every other day dosing.

If at any visit the child's weight is greater than the 95th percentile, the 95th percentile weight in kg will be used to calculate the dose. If this dose reduction is implemented, then additional reductions would not be implemented at that visit for the other dose reduction criteria. At a single visit, if the dose of oxandrolone is reduced for one criterion, then the dosage is not reduced again for another study criterion.

Safety results necessitating stopping the study:

If at any point in the study, two or more patients develop severe liver function changes or hypertension, the study will be stopped. These changes have not occurred with oxandrolone used in a trial with 73 girls with Turner syndrome followed for up to four years and are therefore not expected.

Criteria for Subject Withdrawal from the study and adverse event reporting:

Subjects can withdraw from the study at any time for any reason. The PI may terminate a subject's participation due to severe adverse events, noncompliance with the study, or concerns about safety. Safety data will be reviewed on an ongoing (blinded) basis by the PI.

Study compliance: We will assess patient compliance by having the families fill out study cards when they administer all medications and return the cards as well as all used and

unused study materials at the time of their visit. All pills dispensed and returned will be counted and recorded. We are currently using this procedure in other ongoing studies and have found that it is effective.

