Post-Study Visit: Per the recommendation of the Data Safety and Monitoring Board (DSMB) all study participants will be invited back for a post-study visit. This visit will occur approximately 6-28 months post-study for patients who have enrolled in the study. The post-study visit will include a history, physical examination, fasting blood work, bone age x-ray, photographs, and cognitive testing. Patients will be reimbursed \$50.00 for completion of the visit. Patients who are unable to travel to a post-study visit or who live farther than driving distance will be asked to have a blood sample drawn locally and sent to our office in Philadelphia.

ANALYSIS

The analysis will be performed in consultation with the statistician, [name] who has been collaborating with [name] for the past 15 years. The analyses described below will include 2 groups of KS boys. All results will be based on gender and age-specific standardized scores. Analysis for safety will be performed at 3, 6, 12, 18, and 24 months and an efficacy analysis for summary scores encompassing all cognitive and behavioral variables will be performed at 12 and 24 months.

I. Safety: An analysis of safety parameters will be performed for the 3, 6, 12, 18 and 24 month values based on a two-way ANCOVA, adjusting for baseline values, comparing the active treatment group versus the placebo. The safety parameters are: systolic and diastolic blood pressure, HDL, LDL cholesterol, liver function (ALT), bone age advancement, or signs of puberty (pubic hair).

II. Primary efficacy (Hypotheses 1 a,b,c): The analysis comparing androgen-treated to placebo-treated KS subjects for the one and two-year measurements will be based on the analysis of covariance (ANCOVA). We will perform a two-way ANCOVA for the five primary outcome measures at 12 and 24 months, comparing the treatment group versus the placebo, adjusting for baseline values and socioeconomic status. There will be a total of 5 summary scores. Each score will be the sum of component z-scores based on gender and age-specific normative values. The summary scores include 1. General cognition, 2. Language, 3. Working memory/executive function and attention, 4. Motor function, and 5. Self-image and behavior. The alpha level for statistical significance will be set at 0.01 for each of the five primary outcome results.

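### Participation can be ended for harm or noncompliance with no scheduled follow-up and no missing-data rule, so later safety and efficacy values may be informatively missing

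*Combined protocol and SAP*

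**What the plan says.** All references are to the combined protocol and SAP.

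- **Ending participation.** Procedures, section IV, under the criteria for subject withdrawal and adverse event reporting: "The PI may terminate a subject's participation due to severe adverse events, noncompliance with the study, or concerns about safety". The same paragraph adds "Subjects can withdraw from the study at any time for any reason" and "Safety data will be reviewed on an ongoing (blinded) basis by the PI". It gives no procedure for following an event after a boy leaves.
- **Stopping tablets.** Earlier in section IV a list is headed "Safety results necessitating an approximate 10-50% reduction in medication dose or stopping the medication". It covers bone age, early puberty, blood pressure, lipids and SGPT. It does not say whether visits continue once medication is stopped.
- **Schedule.** Section IV, clinical trial substudy: "All subjects will be evaluated for safety at baseline, 3, 6, 12, 18 and 24 months", with cognitive and behavioural testing after one and two years.
- **Analysis.** Analysis, section I: "An analysis of safety parameters will be performed for the 3, 6, 12, 18 and 24 month values based on a two-way ANCOVA", adjusted for baseline. The parameters are measured quantities and pubic hair. Section II uses ANCOVA for the five summary scores at 12 and 24 months. Neither section defines the boys analysed or the handling of missing values, and neither compares adverse events or terminations by arm.
- **Post-study visit.** All participants are invited back about 6-28 months after the study. For boys who cannot travel, this becomes a locally drawn blood sample. The visit is in no planned analysis.

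**The concern.** The two parts of section IV describe different actions for overlapping reasons. One acts on the tablets and the other on the boy's place in the study. The second has triggers related to harm and adherence, and both arise after randomisation. If the drug causes the harm, the triggers will be met more often on oxandrolone than on placebo.

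Two things are then at stake. The first is knowledge of safety. Whether bone age advance, early pubertal signs, lipid changes or liver enzyme rises persist or resolve off drug is something this trial in boys aged 4-12 could show, and the boys who would show it are the ones whose scheduled visits may end. The second is the randomised comparison. A visit-by-visit ANCOVA with no stated analysis set will in practice use the values that exist, so at later visits it may compare boys selected for tolerating and taking their assigned treatment. The 24-month efficacy comparison is exposed in the same way.

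**Working it through.** **What the plan fixes.** It states no expected number of terminations and no size for this bias, so there is no figure of its own to reproduce. The size below is an illustration on assumed inputs.

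**Assumed inputs.**
- 60 boys per arm: the target of 120 divided by 2. The 1:1 ratio is assumed because it is not stated.
- A normally distributed safety parameter with SD 1, measured at baseline, 12 and 24 months, with correlation 0.6 between visits.
- A true active-minus-placebo shift of 0.3, 0.5 or 0.8 SD at 12 and 24 months.
- A limit at the placebo 95th percentile (1.645). Boys above it at 12 months are terminated. Their 12-month value is kept and their 24-month value is missing.
- The 24-month contrast is estimated by ANCOVA adjusting for baseline, as in Analysis section I.

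**Step 1, who leaves.** The share above the limit is 1 - Φ(1.645 - shift).
- Placebo: 5.0%, or 3.0 of 60.
- Active: 1 - Φ(1.345) = 8.9%, 1 - Φ(1.145) = 12.6% and 1 - Φ(0.845) = 19.9%, or 5.4, 7.6 and 11.9 of 60.

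**Step 2, the 24-month mean contrast when every boy above the limit is terminated** (simulated, one million boys per setting).

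| True shift | Remaining boys only | Everyone followed, harm persists | Everyone followed, half persists | Everyone followed, harm fully reverses |
|---|---|---|---|---|
| 0.3 | 0.282 | 0.301 | 0.287 | 0.274 |
| 0.5 | 0.467 | 0.501 | 0.469 | 0.437 |
| 0.8 | 0.739 | 0.803 | 0.723 | 0.644 |

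- Harm persists: 1 - 0.282/0.301 = 6%, 1 - 0.467/0.501 = 7%, 1 - 0.739/0.803 = 8% understatement.
- Harm fully reverses: 0.282/0.274 - 1 = 3%, 0.467/0.437 - 1 = 7%, 0.739/0.644 - 1 = 15% overstatement.
- Half persists: the two contrasts differ by about 2% or less, and the sign changes across the three shifts.

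The remaining-boys figure is the same in every scenario. What changes is the contrast that complete follow-up would have shown, and the plan collects nothing that would tell which scenario applies.

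**Step 3, fewer terminations, harm persists.**
- Half of the boys above the limit terminated: 0.300 to 0.293, 0.500 to 0.486 and 0.801 to 0.776, an understatement of 2-3%.
- One quarter terminated: 0.298 to 0.294, 0.504 to 0.497 and 0.797 to 0.785, an understatement of about 1.3-1.5%.

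**Step 4, the tail.** With every boy above the limit terminated and the harm persisting, the active-arm share above the limit at 24 months falls from 8.9% to 6.1%, from 12.6% to 8.3% and from 19.9% to 12.6%. These are relative falls of 31%, 34% and 37%, or about one third. The tail is affected far more than the mean.

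**The case against.** Several points count against a strong reading, and most of them stand in part.

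- **The event is not lost.** A reader might infer that the adverse event goes unobserved. It does not: it is the reason for termination, and values up to and including the detecting visit stay in the visit-by-visit analysis. Only the later course and later values can be missing.
- **The rule is discretionary.** It says the PI may end participation, and the list in section IV already offers a route that touches only the medication. The schedule also covers all subjects and does not exclude boys off tablets. So loss is permitted rather than required. But the schedule gives no visit to a boy whose participation has ended.
- **The direction is open.** A reader might infer that the comparison must understate harm. Step 2 shows that this depends on what happens off drug. With full reversal, the remaining boys overstate the contrast from following everyone.
- **The illustration is at the high end.** A blood pressure above the 95th percentile is a listed reason to change the medication, whereas termination is for severe events, noncompliance or safety concerns. The study also stops if two or more patients develop severe liver changes or hypertension, so removals for those events could not accumulate. Deleting the triggering values from the same visit would give a much larger bias, but those values are recorded.
- **The dropout allowance is not a measure of this loss.** Study Population plans recruitment "assuming an approximate 30% drop out rate, to accrue a total of 120 patients for the clinical trial substudy". Nothing ties that general allowance to terminations for safety.
- **The post-study visit helps a little.** It includes examination, blood work, bone age and cognitive testing, but it is late, voluntary and not analysed.

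**Conclusion.** The point holds as a gap in follow-up and analysis, with medium confidence. The protocol lets participation, not only medication, end for reasons related to harm or adherence. It does not keep those boys on the scheduled visits, and it states neither an intention-to-treat set nor a missing-data rule. Their later safety and efficacy values may therefore be informatively missing.

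The size depends on assumptions that the documents do not settle. With correlation 0.6, shifts of 0.3-0.8 SD and every boy above the limit terminated, the mean safety contrast is understated by about 6-8% if harm persists and overstated by about 3-15% if it fully reverses. The share above the limit in the active arm falls by about one third if harm persists. With fewer terminations the effect on the mean is smaller. No figure is available for the efficacy comparison, which is exposed to the same selection in an unknown direction. The documents do not support saying that harm is necessarily understated or that the events themselves go unseen.

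**What to change.** Reconcile the two parts of section IV by separating stopping study medication from leaving the study.

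- **Follow-up.** By default, ask boys whose medication is stopped for safety or noncompliance to continue the scheduled safety visits and the 12 and 24 month testing. The exceptions are withdrawal by the family and study procedures that are themselves unsafe for the boy.
- **Records.** Record the date and reason for each medication stop and each departure from the study as separate items.
- **Analysis.** In Analysis sections I and II, analyse by randomised arm, include values obtained after stopping, and say how values that are still missing will be handled. Add a report of adverse events and terminations by arm.

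When to reduce or stop medication stays with the sponsor and is not touched by this change.

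The cost is a short amendment and a few off-drug visits using assessments already planned. Off-drug values may slightly dilute the efficacy estimate, which would then describe the effect of assignment to oxandrolone rather than of taking it throughout.

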Klinefelter's syndrome (KS), first described in 1942 on the basis of testicular failure (1), occurs only in males, and is characterized by the abnormal chromosome karyotype 47,XXY (2). Unlike other chromosomal trisomies, 47,XXY does not frequently cause spontaneous abortuses, most likely related to inactivation of the supernumerary X-chromosome occurring in many tissues. The KS phenotype includes testicular failure, tall stature, and a characteristic cognitive and behavioral phenotype. Other KS-associated phenotypic findings include increased risk for osteoporosis, breast cancer, autoimmune thyroid disorders, and Type II diabetes mellitus (3). Most KS males were previously diagnosed in adolescence on the basis of testicular failure; however, increasing numbers are now detected through routine antenatal testing. Approximately 1 per 500-1000 males are affected (4). Mosaicism for a normal 46,XY line occurs in approximately 10-20% of KS cases and is associated with improved prognosis.

I. Testicular failure phenotype

The clinical spectrum for the testicular failure phenotype ranges from near complete androgen deficiency and gonadal failure starting prenatally to mild androgen deficiency with azoospermia in adulthood. Many KS boys have fetal onset of gonadal failure manifest by small testes and penis early in infancy or childhood and early symptoms of androgen deficiency. Others manifest testicular failure in adolescence or adulthood. The in utero testosterone deficiency would likely occur in the last trimester because testosterone deficiency earlier in gestation would result in ambiguity of the external genitalia with hypospadias, which is not characteristic of KS. Rather, a burst of testosterone synthesis in the last trimester stimulates penile growth and it is this later testosterone growth-stimulating effect on the genitalia that is missing in KS males.

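### The planned between-arm safety comparison leaves out acne, voice change, growth, fasting glucose and blood count, although all are monitored or collected

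*Combined protocol and SAP*

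**What the plan says.** The combined protocol and SAP has one between-arm safety analysis, in ANALYSIS, part I. Its method is "based on a two-way ANCOVA, adjusting for baseline values, comparing the active treatment group versus the placebo". Its timing is given just above: "Analysis for safety will be performed at 3, 6, 12, 18, and 24 months". Its content is a list with no wording such as 'including': "The safety parameters are: systolic and diastolic blood pressure, HDL, LDL cholesterol, liver function (ALT), bone age advancement, or signs of puberty (pubic hair". The bracket narrows signs of puberty to pubic hair.

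The clinical trial substudy (Procedures, part IV) collects and watches more than this. It calls the visits at baseline and at 3, 6, 12, 18 and 24 months safety evaluations. Its follow-up schedule measures height and weight and draws "fasting blood work to include complete blood count, serum glucose, liver function tests (SGPT), lipid panel, thyroid studies, testosterone, and free testosterone". On androgen effects it says "Children will be monitored closely for signs of virilization including acne, voice changes", and the same sentence goes on to pubic hair and excessive bone age advancement. The list of safety results that can lower the dose ends with item 8: "Dose can be lowered at the discretion of the investigator for other reasons such as rapid growth".

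**The concern.** The trial gives an androgen to boys aged 4 to 12. By its own account (Specific Aims), androgen replacement has not been used this early in Klinefelter's syndrome, and a positive result is meant to move the start of treatment to early childhood. The safety experience it cites comes mainly from other groups: girls with Turner syndrome and boys with delayed puberty. The randomised comparison is therefore the main safety evidence for this population.

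That comparison is prespecified for only part of what the protocol treats as worth watching. An excess of acne or voice change on oxandrolone, or a difference in growth, glucose or haemoglobin, has no assigned place in the safety results. Whether it is reported by arm would be decided after the data are in, which leaves room for selective safety reporting.

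**Working it through.** The documents give no sample size, power or significance level for safety, so there is no figure to reproduce. The check is a comparison of sections, followed by a count.

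**Step 1. Match the analysed list to the dose-reduction list (Procedures, part IV).**

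| Dose-reduction criterion | In the between-arm analysis? |
|---|---|
| 1. Bone age advancement | Yes |
| 2. Early pubertal signs, including pubic hair | Yes, as pubic hair |
| 3. Systolic blood pressure | Yes |
| 4. Diastolic blood pressure | Yes |
| 5. LDL cholesterol | Yes |
| 6. HDL cholesterol | Yes |
| 7. SGPT (ALT) | Yes |
| 8. Investigator discretion, example rapid growth | No |

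Seven of eight criteria are covered. The one left out concerns growth, for which height and weight are measured.

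**Step 2. Match it to the named virilization signs.** Four are named: acne, voice change, pubic hair and bone age advancement. The last two are analysed and the first two are not.

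**Step 3. Match it to the fasting blood sample.** ALT and the lipids from this sample are compared by arm. Glucose and the blood count from the same sample are not. The schedule wording (baseline, three months, then six-monthly) is read here as the safety visits at 3, 6, 12, 18 and 24 months.

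**Step 4. Look for another analysis that covers the missing items.**
- ANALYSIS has only two parts, safety and primary efficacy. The five efficacy scores are general cognition, language, working memory, motor function and self-image. None contains the missing items.
- The PI's ongoing safety review (section on subject withdrawal and adverse events) is blinded, so it does not compare arms.
- Data Management and processing promises summary tables but states neither their content nor a split by arm.
- A DSMB is mentioned under Post-Study Visit, with no description of what it receives.

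**Step 5. Count.** Five items are monitored or collected without a prespecified comparison: acne, voice change, growth, glucose and blood count. The current plan has 7 parameters × 5 visits = 35 comparisons. Treating the five missing items in the same way would give 12 × 5 = 60.

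**Step 6. Multiplicity if every comparison were tested.** Assume a 0.05 level for each test and independence; the documents state neither. The chance of at least one false positive is 1 − 0.95^35 = 0.834 now and 1 − 0.95^60 = 0.954 after the addition. Repeated measures on the same boys are correlated, so these figures are illustrative. They argue for estimates rather than more tests.

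**The case against.** The best defence is that the list follows a rule. Its seven items are those with a stated dose-reduction trigger, and the only unmatched criterion is discretionary. Virilization is not ignored either, since pubic hair and bone age are compared. This explains how the list arose. It does not explain why two signs named in the same sentence as pubic hair and bone age are left out, or why growth is left out when it can lead to a lower dose.

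Second, not every missing item carries a safety label. Acne, voice change and rapid growth do. Glucose and blood count have no threshold, and their safety role is inferred from being drawn at visits described as safety evaluations. Height is also filed under Study Outcome as a physical feature. This stands, so the case is firmest for the first three items.

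Third, more items mean more chance findings. This also stands, and it shapes the fix.

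Two stronger readings are tempting. A reader might infer that an effect on these items would never be compared with placebo. The documents show only that no comparison is prespecified: the data are recorded for each boy, tables of unstated content are planned, and a DSMB exists. A reader might also lean on the Background, which gives boys with this syndrome an "increased risk for osteoporosis, breast cancer, autoimmune thyroid disorders, and Type II diabetes mellitus". Both arms share that risk, and the documents do not say that oxandrolone changes glucose, haemoglobin or thyroid function. Thyroid tests are explained under Laboratory studies by disease risk, so they are not part of this point.

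**Conclusion.** The point holds as a gap in the completeness of the safety comparison. The prespecified analysis covers seven parameters. It omits two of four named virilization signs, the growth measure behind one of eight dose-reduction criteria, and two results from a blood sample whose ALT and lipids are compared by arm. No other planned analysis fills the gap. Primary efficacy is unaffected.

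The conclusion rests on reading the safety list as closed, which its wording supports, and on treating the safety-visit bloods as safety data, which is an inference for glucose and blood count. It does not rest on power. A reader might want to state how large a shift the omitted measures could detect, but that would need an allocation ratio, complete data and baseline correlations that the documents do not give. Such a figure would also say nothing about signs recorded as present or absent.

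**What to change.** In ANALYSIS, part I, extend the safety list in two ways.

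- Add height z-score, weight (or BMI) z-score, fasting glucose and haemoglobin or haematocrit. Report each as a baseline-adjusted difference between arms with a 95% interval at 3, 6, 12, 18 and 24 months, as estimates without significance claims.
- Tabulate the number of boys with new acne and with new voice change by randomised arm. Counts suit these signs better than ANCOVA if they are recorded as present or absent.

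The additions come to 4 × 5 = 20 estimates beside the existing 35, plus two sets of counts. They need no extra visit, blood draw or staff. The documents do not show the case report form; if it has no field for acne and voice change at baseline and follow-up, one must be added. The downside is a few more tables and more comparisons to read with caution.
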